#### 5.1 Study Design

Briefly, in Pilot Trial A, all will be first given the usual English PML for their new medication. There may be non-standardized, ad-hoc noting on the PML by the pharmacy staff when participant is deemed not able to understand the English PML. All content of the non-standardized, ad-hoc noting including pictures drawn will be recorded. Then, *at 2 weeks post-recruitment*, their baseline level of the 3 medication-related outcomes (w.r.t. the new medication) will be gauged, after which they will be *randomized* (1:1; block randomization, block of 4) to one of 2 PMLs (Bilingual [intervention] or English [usual care]) at their home. Follow-up assessment of the 3 medication-related outcomes will be also be done at 2 weeks post-randomization at their home.

In Pilot Trial B, participants will be *randomized* (1:1; block randomization, block of 4) *just after recruitment* to one of 2 PMLs (Bilingual [intervention] or English [usual care]) in the DMC pharmacy. There may be non-standardized,ad-hoc noting on the PML by the pharmacy staff when participant is deemed not able to understand the English PML. All content of the non-standardized, ad-hoc noting pictures drawn will be recorded. The 3 medication-related outcomes will be assessed at 2 weeks post-randomization at their home.

All participants will receive their usual medical care, and usual medication counselling at the DMC pharmacy for all their medications. All medications, other than the new oral medication (which made them eligible, and whose PML will be intervened upon), will be dispensed with usual English PMLs.

#### 5.1.1 Modified Study Design In View Of COVID-19

In view of COVID-19 restrictions imposed as of 16 August 2021, a portion of the Main Questionnaire will be done via phone call instead of fully relying on home visits. The study staff

will conduct a home visit to complete the remaining questions from the Main Questionnaire and collect data from the Rx  $Cap^{TM}$  bottles, with a time limit of 20 minutes to keep participants and staff safe.

Additionally, should any participants be subjected to COVID-19 Stay Home Notices or Quarantine Orders, participation will immediately be forfeited for the safety of participants and study staff. Retrieval of the Rx CapTM bottle and delivery of remaining medicines will be arranged in a proper manner in accordance to any guidelines set by the SGH Research Office and MOH.

#### 5.2 Study Methodology

Bilingual PMLs (Intervention): Bilingual PMLs, for common medications at the DMC pharmacy, which "mirror" medication instructions on the corresponding English PMLs, will be developed by the investigator team. While the Health Products (Therapeutic Products) Regulations 2016 mandate English PML provision, there is no restriction to adding another language. In fact, some polyclinics already print PMLs in their patients' preferred language, upon request, to supplement English PMLs.

Randomization: All 3 block randomization sequences (Pilot Trial A or B, then, study arm within each Pilot Trial) will be generated a priori. After a participant gives consent, project staff will be informed of his/her allocation to Pilot Trial A or B. For those in Pilot Trial A, further assignment to study arm will be disclosed only after the baseline level of the 3 medication-related outcomes is assessed at 2 weeks post-recruitment. For those in Pilot Trial B, assignment to study arm will be disclosed immediately, as there is no baseline assessment of the 3 medication-related outcomes.

Covariates: A range of socio-demographic and medication-related (e.g. no. of medications, help received in medication management) variables will be collected, using a questionnaire, at recruitment.

Medication-related outcomes: They will be gauged at 2 weeks post-recruitment and 2 weeks post-randomization for those in Pilot Trial A, and at 2 weeks post-randomization for those in Pilot Trial B.

#### 5.2.1 Measurements

Medication adherence: It will be measured in 4 different ways:

- 1. Adherence to Refills and Medications Scale (ARMS): A validated self-reported medication-adherence scale intended for patients with chronic diseases. The 12-item questionnaire consists of 2 sub scales adherence to refilling prescriptions and adherence with taking medications. Each item is structured using the Likert scale, with the following response options and corresponding scores: "none" (score of 1), "some" (score of 2), "most" (score of 3), or "all of the time" (score of 4). The range of possible total scores is 12 to 48. Lower scores indicate better adherence.
- 2. MedTake Assessment: A self-reported measure, recommended by Ministry of Health, Singapore for pharmacy staff when they provide pharmaceutical care services, that assesses patient adherence and knowledge to dose, dosage, indication, food or water coingestion, and regimen. A composite score (0–100%; higher ~ better) summarizes patient's ability to take medication safely.
- Pill count: A pill count, in context of the new oral medication, will be done.
  % adherence= ((quantity dispensed)-(quantity remaining))/((prescribed number of pills per day)×(no.of days between dispensing date and interview))

Electronic medication packaging [EMP]: All participants will be dispensed their new oral

medication in a Rx CapTM medication bottle (www.rxcap.com), whose Rx CapTM Bluetooth smart cap will automatically track medication usage every time it is opened. Project staff will sync participants' data, collected and stored within the Smart Cap, at each home visit, and import it to the Rx CapTM Engage platform for analysis. Continuous (% adherence to prescribed regimen; 0-100%) and categorical variables (not at all; partially; fully) for medication adherence will be derived. Rx CapTM medication bottle is not being used in standard clinical practice yet and it is used for this proposed research only. To our best knowledge, Rx CapTM medication bottle is not validated for use clinically yet.

Medication management self-efficacy: The 8-item Medication Understanding and Use Self-Efficacy Scale (MUSE), comprising 2 subscales – (1) taking medication (4 items), and (2) learning about medication (4 items), will be used. Item scores (four-point Likert scale; strongly disagree (score=1), to, strongly agree(score=4)) will be summed for subscale (range: 4-16) and total (range: 8-32) scores.

PML understanding: It will be assessed by asking questions adapted from a local study (led by the mentor) assessing this construct among elderly Singaporeans. Respondents will be asked tailored questions (in their preferred language) specific to the instructions presented on their PML for the new oral medication, for instance "How many times a day do you have to take this medication?". Each question will be marked as "correct" or "incorrect". Continuous (% correct responses; 0-100%) and categorical variables (none; partial; complete) for PML understanding will be derived.

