Need for rigorous PML intervention studies: A recent review on the impact of improved PMLs concluded that intervention studies that test PML improvements in a rigorous manner are lacking. It also recommended that future studies should extend research to outcomes more proximal to medication taking – medication adherence and medication management self-efficacy. In Singapore, the only published PML intervention did show bilingual PMLs (vs English PMLs) to increase PML understanding. However, it, again, did not assess medication adherence and medication management self-efficacy. Thus, rigorous intervention studies that assess the impact of improved PMLs on a range of medication-related outcomes are needed.

Our proposal is the *first step* towards a well-informed, rigorous intervention study or RCT that will provide concrete evidence on the impact of the provision of bilingual PMLs on key medication-related outcomes – medication adherence, medication management self-efficacy, and PML understanding. The experience gained, and data collected, through the conduct of the 2 pilot trials, funded through the current proposal, will allow us to choose the optimal trial design, and refine protocols for recruitment, engagement and retention of study participants for the larger RCT as well as determine variability in outcomes so that the larger RCT is appropriately powered to detect meaningful differences in the outcomes – an immediate output of our proposed project will be a grant proposal to a national level grant mechanism for the conduct of the larger RCT. Eventually, the 2 pilot trials, and the subsequent larger RCT, will contribute to implementing patient-centered PMLs.

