#### 4.3. Inclusion Criteria

[figure not shown]
(1) Singapore Chinese citizen/permanent resident; (2) age  $\geq$ 50 years; (3) just received a new (i.e., not received before) oral medication for a chronic disease from DMC pharmacy; (4) no moderate/severe cognitive impairment ( $\geq$ 5 correct responses on the Abbreviated Mental Test, AMT); (5) not deaf (self-reported); (6) no binocular presenting near vision impairment (near visual acuity, with routinely used spectacles/lenses: at least 6/15 (0.40 logMAR) on the Landolt's C chart); (7) able to speak English and/or Mandarin; (8) unable to read in English but able to read Mandarin (as they will benefit the most from bilingual PMLs); (9) assessed as non-adherent as per 2 questions - "In the last one month, how often did you take your medications?" (as they will benefit the most from an intervention aimed at improving medication adherence).

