# 8.2. Statistical and Analytical Plans

As we are conducting 2 "pilot" versions of a RCT, most analyses will be descriptive and exploratory. In both pilots, trial outcomes will be summarized using measures of central tendency and dispersion (e.g., mean and standard deviation). In Pilot Trial A, significant difference in change, from baseline to 2 weeks post-randomization, in the 3 medication-related outcomes between the 2 arms will be assessed using t-test (for continuous variables, e.g. difference in change in ARMS

scores or MUSE scores) or chi-square test (for categorical variables, e.g. difference in change in % with complete PML understanding or % with complete adherence as per EMP). In Pilot Trial B, significant difference, at 2 weeks post-randomization, in the 3 medication-related outcomes between the 2 arms will be assessed using t-test (for continuous variables, e.g. difference in the ARMS scores or MUSE scores) or chi-square test (for categorical variables, e.g. difference in % with complete PML understanding or % with complete adherence as per EMP). For agreement between medication adherence assessed using EMP and that assessed using the 3 other approaches, Bland-Altman plots (adherence considered as continuous) and Cohen's kappa43.45 ( $\varkappa$ ; adherence considered as categorical) will be used. While our findings will only provide a general sense of the intervention impact, they will primarily inform which measures to use for the subsequent RCT and for determining its optimal sample size. We will also tabulate participation rates and loss to follow-up.

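### Pilot Trial A's follow-up pill count runs from dispensing, so it re-uses the two pre-randomisation weeks and, on the stated schedule, halves the change from baseline and its SD

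*Protocol*

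**What the plan says.** Section 5.2.1 defines pill-count adherence once, for all assessments. The numerator is "quantity dispensed)-(quantity remaining", so it accumulates from the day of supply. The denominator is the prescribed pills per day times the "no.of days between dispensing date and interview".

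The Pilot Trial A timeline comes from three places:

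- Section 4.3 requires that the patient has "just received a new (i.e., not received before) oral medication for a chronic disease from DMC pharmacy", so dispensing is at day 0.
- Section 5.1 says that in Pilot A "all will be first given the usual English PML for their new medication".
- Section 5.2 says of the outcomes, "They will be gauged at 2 weeks post-recruitment and 2 weeks post-randomization for those in Pilot Trial A", and that "further assignment to study arm will be disclosed only after the baseline level of the 3 medication-related outcomes is assessed at 2 weeks post-recruitment". Baseline and randomisation therefore fall at about day 14 and follow-up at about day 28.

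Section 8.2 analyses Pilot A as change: "significant difference in change, from baseline to 2 weeks post-randomization, in the 3 medication-related outcomes between the 2 arms will be assessed using t-test". Section 1 says the pilots should "determine variability in outcomes so that the larger RCT is appropriately powered to detect meaningful differences in the outcomes".

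**The concern.** The formula suits Pilot Trial B, where the arm is assigned at dispensing and the only assessment is two weeks later. In Pilot A it fits the baseline assessment but not the follow-up. By then the count has been running since day 0, so the follow-up value averages the period under the randomised label with the earlier period when everyone had the English label. That earlier period is already the baseline value, so subtracting baseline leaves only part of the real change.

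At stake are the mean change, the between-arm difference in change and the SD of change for pill count in Pilot A. These are the raw quantities a pilot passes to the design of the next trial. Pilot A and Pilot B pill counts would also not be comparable: B's is wholly post-randomisation, while A's is about half pre-randomisation.

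**Working it through.** The protocol states no SD, effect size or power, so there is no figure of its own to reproduce. The check applies its formula to its schedule.

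**Inputs.** d1 = days from dispensing to the baseline count (14 on schedule). d2 = days from the baseline count to follow-up (14 on schedule). b and p = true adherence in those two periods. Prescribed pills per day are taken as constant, with no new supply or reset of the count at randomisation, since none is described.

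**Formula applied.**

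- Baseline = b.
- Follow-up = (d1·b + d2·p)/(d1 + d2).
- Change = follow-up − b = (p − b) × d2/(d1 + d2).

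For 14 + 14 days, follow-up = (b + p)/2 and change = (p − b)/2. A true 20-point between-arm difference in change is reported as 10.

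**Example**, one pill a day: 10 of 14 taken before randomisation and 14 of 14 after.

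- Baseline: 10/14 = 71.4%.
- Follow-up by the formula: 24/28 = 85.7%, although adherence after randomisation was 100%.
- Change by the formula: 85.7 − 71.4 = 14.3 points. True change: 100.0 − 71.4 = 28.6 points.

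**Visits off schedule.** 14 then 10 days gives 10/24 = 0.42; 10 then 14 days gives 14/24 = 0.58.

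**Effect on the t-test.** With equal periods every change score is halved, so the mean difference and its SD scale together. A large simulation (true difference 15 points, SD 20 in each period, correlation 0.5) gave a difference of 7.5 against 15.1 points, an SD of change of 10.0 against 20.0 points, and identical t statistics. With each period varied between 12 and 17 days, t fell only from 237.4 to 236.2.

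**Follow-up value on its own.** With equal SDs in the two periods and correlation ρ (assumed), its SD is multiplied by √((1+ρ)/2): 0.71, 0.87 and 0.95 for ρ = 0, 0.5 and 0.8. The expected between-arm difference is halved. The standardised difference therefore falls to 0.5/0.707 = 0.71 of its true value at ρ = 0 and 0.5/0.949 = 0.53 at ρ = 0.8. Here the scaling does not cancel.

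**Larger trial, conditional.** Assume a 10-point target in real adherence points, 80% power and two-sided 5%, with n per arm = 2 × (1.960 + 0.842)² × (SD/10)².

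| True SD of change | n per arm, true SD | n per arm, halved SD |
|---|---|---|
| 15 | 36 | 9 |
| 20 | 63 | 16 |
| 25 | 99 | 25 |

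A trial sized from the last column would have about 29% power. If the effect and the SD are both taken from the pilot, both are halved and n is unchanged: SD 10 with a target of 5 gives 63.

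**The case against.** The strongest reply is that the dilution rests on silence. The protocol does not describe how the new label reaches the patient at the home visit, and section 7.2 allows one or two tracker bottles per participant. If a fresh bottle were dispensed at randomisation, the dispensing date would move and the formula would be right. But nothing ties the second bottle to randomisation. Section 5.1 randomises the patient to a label at home and mentions no new supply or restart of the count. If a reset is intended, one sentence would settle it.

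It can also be said that derivation windows belong in the SAP. That would answer a missing detail, but here the formula is stated and gives the wrong quantity on the stated schedule.

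The points about consequence largely stand. The t statistic is unchanged with equal periods. Pill count is one of four adherence measures and is not among the examples named in section 8.2, though those are only examples. The analyses are mostly descriptive, with about 10 patients per arm (40/2/2). The correct value can be recovered from the two counts. Mis-sizing the larger trial needs the shrunken SD to be paired with an outside target, a pairing the protocol does not plan. A cumulative pill count compared with electronic monitoring over the same days would still be a valid agreement analysis.

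**Conclusion.** The concern holds: as written, the formula gives the wrong follow-up adherence for Pilot Trial A. The change from baseline and its between-arm difference are multiplied by d2/(d1 + d2), exactly 0.5 for two 14-day periods and 0.42 to 0.58 for the four-day slippages shown. The SD of change is halved with equal periods. This assumes constant prescribed pills per day and no restart of the count at randomisation.

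The change-score test itself is not invalidated. The damage is to the raw effect and SD handed to the larger trial, to the Pilot A follow-up value, and to comparability with Pilot B. The sample-size figures illustrate a conditional risk and depend on an assumed target and SDs. This should be fixed, but it does not threaten the pilot as a whole.

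**What to change.** Keep the present formula for the Pilot A baseline and for Pilot B. For the Pilot A follow-up, replace it with:

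(pills remaining at the baseline count + any pills supplied since − pills remaining at the follow-up count) / (prescribed pills per day × days between the two counts).

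Take the days from the dates on which the pills are physically counted. Section 5.1.1 splits the questionnaire between a phone call and a home visit, so the interview date can be read two ways. If the plan is instead to dispense a new supply at randomisation and count from there, say so.

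The cost is one rewritten formula. Pilot A already assesses adherence, including pill count, at both time points, so no extra visit or data item is needed. Counts already taken can be re-derived if their dates were recorded.

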#### 2. HYPOTHESIS AND OBJECTIVES

Since the proposed study will collect preliminary data for informing the larger RCT, it does not aim to detect a significant difference in the trial outcomes in either pilot trial. Rather, its specific aims are:

AIM 1. To assess the feasibility of administering the intervention in the 2 "pilot" RCT versions. The proposed formative study will inform which of the 2 pilot trials will be scaled up and tested in the larger RCT. It will also result in finalization of the intervention and measurement material. AIM 2. To refine protocols for study participant recruitment, engagement and retention. AIM 3. To gain experience with and refine measurement of the medication-related outcomes.

A key outcome, medication adherence, will be measured using several approaches – self-report (ARMS; MedTake Assessment), which is easier and cheaper, and objective (pill count; electronic medication packaging [EMP]), which is tedious and expensive – during the 2 pilot trials. Comparison of the various approaches against the EMP (the most objective approach) will inform the choice of the measurement approach to be used for medication adherence in the larger RCT.

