# 7.2. Data Entry and Storage

All data with personal identifiers will be encrypted with password-protection. All physical research data including consent forms, data entry forms will be stored in locked cabinets at SGH. All soft copy research data will be coded, with participants' identifiers stored separately from research data, and only available on computers within the institution. Only de-identified data will be shared with study team members for data analysis and only the investigators and authorized personnel (principal investigator, co-investigators and research assistant) directly involved with the study will have access to the data. After study completion, research data will be stored on institution computers and remain password-protected, for a minimum of 7 years after completion of research study or date of publication of the research using the research data, whichever is later.

The Rx CapTM bottle measures patients medication adherence (Adherence is considered "met" when the new oral medication is taken based on both prescribed number of times per day and prescribed time of the day), each participant will be given 1-2 Rx CapTM pill tracker bottles. The electronic cap of the pill tracker records the date and time when the patient opens the vial to take his/her medication. This bottle does not collect any personal identifiers. A Rx CapTM account would be created for each participant. However, these accounts will be created by the study team using non-identifiable user information (i.e., "dummy" email addresses/usernames). As such, no personal identifiers will be stored in third-party databases.

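### Agreement is planned only against an unvalidated cap that reads openings as use, so disagreement cannot be traced to the cap or to the other measure

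*Protocol*

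**What the plan says.** Section 5.2.1 lists four adherence measures: ARMS, MedTake, pill count and EMP. For EMP, the smart cap "will automatically track medication usage every time it is opened". Section 7.2 makes the same link between opening and dosing: the cap "records the date and time when the patient opens the vial to take his/her medication". Section 7.2 also sets the scoring rule. Adherence is met when the drug is "taken based on both prescribed number of times per day and prescribed time of the day". Section 5.2.1 adds that, to the investigators' knowledge, the "medication bottle is not validated for use clinically yet".

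Section 2 gives EMP its role: "Comparison of the various approaches against the EMP (the most objective approach) will inform the choice of the measurement approach" for the larger RCT. Section 8.2 carries this out: "For agreement between medication adherence assessed using EMP and that assessed using the 3 other approaches", it plans Bland-Altman plots and Cohen's kappa. It lists no pair that leaves EMP out. It also says that the findings will primarily inform the choice of measures and the sample size of the next trial.

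Staff sync the cap at each home visit. The pill count concerns the same new drug and uses the quantity remaining. The protocol does not mention pills being moved to another container, openings for reasons other than dosing, or the order of syncing and counting.

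**The concern.** An opening is a proxy for a dose. It fails when several doses are taken out at once, when the bottle is opened and nothing is taken, or when someone other than the participant opens it. The protocol acknowledges that the device is unvalidated, yet uses it as one half of every planned comparison.

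If EMP disagrees with pill count, ARMS and MedTake, the cap may be wrong, or the others may be. Three comparisons that share one member cannot separate these cases. Aim 3 is to refine the measurement of the outcomes, and section 8.2 treats the choice of measures as a main product of the pilot. Ambiguity here therefore touches something the study is meant to deliver.

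Timing also matters. Whether pills were moved, and when staff opened the bottle, can be recorded only at the visit. A later analysis plan cannot recover what the visit form did not capture, and section 5.1.1 limits the home visit to 20 minutes.

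**Working it through.** The plan has no agreement figure to reproduce, and section 8.1 says that no sample size estimation was done. What follows illustrates possible size; it is not an estimate.

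**From the protocol:** 40 participants (section 4.1); assessments at 2-week intervals (section 5.2); pill-count adherence = (dispensed − remaining) / (prescribed pills per day × days); EMP on a 0 to 100% scale (section 5.2.1).

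**Assumed, not in the protocol:** EMP % = openings / prescribed doses, capped at 100%; once- or twice-daily dosing; a 14-day window; a participant who takes every dose, so that the pill count is 100%; one staff opening per home visit.

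**Step 1: one participant who moves pills**
- Weekly, once daily: 2 openings / 14 doses = 14.3%; difference EMP − pill count = 14.3 − 100 = −85.7 points.
- Weekly, twice daily: 2/28 = 7.1%; difference −92.9.
- One day's doses taken out together, once daily: 14/14 = 100%; difference 0.
- One day's doses taken out together, twice daily: 14/28 = 50%; difference −50.

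The time-of-day rule in section 7.2 does not rescue the weekly once-daily case, because two openings can satisfy at most two of the 14 days.

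**Step 2: Bland-Altman limits in 40 people**

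Let a share p have d = −85.7, and let everyone else agree exactly. Mean = p·d; SD = |d|·√(p(1−p)·40/39); limits = mean ± 1.96·SD.
- 0 of 40: mean 0, limits 0 to 0.
- 2 of 40: mean −4.3, SD 85.7 × √(0.05 × 0.95 × 40/39) = 18.9, limits −41 to +33.
- 4 of 40: mean −8.6, SD 85.7 × √(0.10 × 0.90 × 40/39) = 26.0, limits −60 to +43.

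Nobody in this example has a positive difference. The positive upper limits arise from fitting symmetric limits to a few large negative values.

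**Step 3: one staff opening in 14 days**
- If any opening counts as a dose and EMP is below 100%: +1/14 = +7.1 points (once daily) or +1/28 = +3.6 points (twice daily).
- If EMP is already capped at 100%, or the opening falls outside the dosing time: 0.
- If an extra opening makes that day fail: −1/14 = −7.1 points.

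**Step 4: which pairs are planned**

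Four measures form 4 × 3 / 2 = 6 pairs. Section 8.2 plans the three that contain EMP. Pill count with MedTake, pill count with ARMS, and MedTake with ARMS are absent.

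**The case against.** The strongest reply is that moving pills is conjecture. The protocol mentions no pill organisers. Recording help with medication management as a covariate (section 5.2) does not show that helpers empty the bottle. The limits in Step 2 also need participants with perfect intake and no other disagreement, whereas section 4.3 enrols people assessed as non-adherent. All of this stands: the figures show what could happen, and zero is equally consistent with the text.

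A reader might infer that each disagreement will be held against pill count or self-report, so that correct pill counts will look wrong. The protocol does not say so. Bland-Altman plots and kappa assign error to neither method, section 2 says only that the comparison will inform the choice, and no rule rejects a measure for disagreeing with EMP. An 86-point outlier would be plain on the plot. What remains is that an outlier can be seen but not explained.

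A reader might also rank staff openings alongside moved pills. That they occur is an inference from the count and the sync both taking place around home visits. Their effect is small, its direction depends on scoring, and the time-of-day rule in section 7.2 may discard them.

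Finally, data cleaning is commonly left to an analysis plan, which is not shown. That covers derivation rules. It does not cover the choice of EMP as sole comparator, which the protocol fixes, or facts that must be recorded at the visit.

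**Conclusion.** The point holds in a limited form. The protocol places a device that it calls unvalidated, and whose openings it equates with use, in every planned agreement analysis, and it describes that device as the most objective measure. Openings that are not single doses can then produce disagreement that the plan cannot trace to its source.

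The size is unknown. Under the stated assumptions a single participant can differ by 86 points, and 2 to 4 such participants among 40 would widen the limits to −41 to +33 or −60 to +43. With none the effect is zero. Staff openings add at most about 4 to 7 points either way.

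It would go too far to say that the pilot cannot choose a measure. Section 8.2 calls most analyses descriptive and exploratory, and section 2 also mentions ease and cost. The weakness reduces what the comparison can tell the investigators; it does not void it. It is worth correcting because the correction costs very little and part of it cannot be made afterwards.

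**What to change.** 1. **At each home visit**, sync the cap before anyone opens the bottle. Record the time of each staff opening and remove it from the EMP series.
2. **Ask every participant**, whatever the EMP and pill-count values, whether pills were moved to another container. Report EMP agreement in all participants as the main result, with a sensitivity analysis that leaves out those who report moving pills. Do not exclude on the EMP-pill count discrepancy itself: that selects on the quantity being measured and inflates agreement. Pills discarded before a visit would leave the same pattern, although there the pill count is the measure in error. The answer is itself self-reported, which is why this analysis should stay secondary.
3. **In section 8.2**, describe the comparison as agreement between measures, not accuracy against EMP, and add the three pairs without EMP. Use Bland-Altman only for measures on the same percentage scale. Where scales differ, use rank correlation or kappa on categories. ARMS runs from 12 to 48 with lower scores better, so limits of agreement between it and a percentage have no meaning. The added pairs do not establish accuracy, but they show whether the other measures cohere when EMP stands apart.

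The cost is one question, one time entry, a few more tables and a slightly smaller sensitivity set. No device, visit or participant is added.
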